APPENDIX 4: EORTC Questionnaire H&N35 (version 1.0)and EORTC QLQ-C30 (version 3.0)

EORTC QLQ - H&N35

Patients sometimes report that they have the following symptoms or problems. Please indicate the extent to which you have experienced these symptoms or problems during the past week. Please answer by circling the number that best applies to you.

Du	ring the past week:	Not at all	A little	Quite a bit	Very much
31.	Have you had pain in your mouth?	1	2	3	4
32.	Have you had pain in your jaw?	1	2	3	4
33.	Have you had soreness in your mouth?	1	2	3	4
34.	Have you had a painful throat?	1	2	3	4
35.	Have you had problems swallowing liquids?	1	2	3	4
36.	Have you had problems swallowing pureed food?	1	2	3	4
37.	Have you had problems swallowing solid food?	1	2	3	4
38.	Have you choked when swallowing?	1	2	3	4
39.	Have you had problems with your teeth?	1	2	3	4
40.	Have you had problems opening your mouth wide?	1	2	3	4
41.	Have you had a dry mouth?	1	2	3	4
42.	Have you had sticky saliva?	1	2	3	4
43.	Have you had problems with your sense of smell?	1	2	3	4
44.	Have you had problems with your sense of taste?	1	2	3	4
45.	Have you coughed?	1	2	3	4
46.	Have you been hoarse?	1	2	3	4
47.	Have you felt ill?	1	2	3	4
48.	Has your appearance bothered you?	1	2	3	4

Please go on to the next page

Dur	ring the past week:	Not at all	A little	Quite a bit	Very much
49.	Have you had trouble eating?	1	2	3	4
50.	Have you had trouble eating in front of your family?	1	2	3	4
51.	Have you had trouble eating in front of other people?	1	2	3	4
52.	Have you had trouble enjoying your meals?	1	2	3	4
53.	Have you had trouble talking to other people?	1	2	3	4
54.	Have you had trouble talking on the telephone?	1	2	3	4
55.	Have you had trouble having social contact with your family?	1	2	3	4
56.	Have you had trouble having social contact with friends?	1	2	3	4
57.	Have you had trouble going out in public?	1	2	3	4
58.	Have you had trouble having physical contact with family or friends?	1	2	3	4
59.	Have you felt less interest in sex?	1	2	3	4
60.	Have you felt less sexual enjoyment?	1	2	3	4
Dur	ring the past week:			No	Yes
61.	Have you used pain-killers?			1	2
62.	Have you taken any nutritional supplements (excluding vitamins	s)?		1	2
63.	Have you used a feeding tube?			1	2
64.	Have you lost weight?			1	2
65.	Have you gained weight?			1	2

[©] Copyright 1994 EORTC Quality of Life Study Group, version 1.0 All rights reserved

EORTC QLQ-C30 (version 3)

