The EORTC quality of life questionnaire is an integrated system for assessing the health-related quality of life (QoL) of cancer patients. There is a set of 30 core questions (QLQ-C30) [4], supplemented by a HNC specific module (H&N 35) [5]. H&N35 is a diagnosis-specific module designed to be used in conjunction with the QLQ-C30 and is intended for use among a wide range of HNC patients, varying in disease stage and treatment modality. The QLQ-C30 contains 30 items which comprise five functional scales, three symptom scales, a global health status scale, and six symptom items. With the exception of the global health status questions, possible question responses range from 1 (not at all) to 4 (very much); for the global health status these range from 1 (very poor) to 7 (excellent). Each of these may be transformed into a score in the range 0-100. Higher scores on the global health status / QoL scale represent better quality of life, higher scores on the QLQ-C30 summary score represent higher levels of functioning and lower symptomology, and higher scores on the H&N35 symptom scales/items represent greater symptomology/more problems.

Based on published scoring guides [6, 7], 13 out of the 15 'scores' computable from the QLQ-C30 (i.e., excluding the 'global health status/QoL' score and the 'financial difficulties' symptom score) may be summarised as a 'QLQ-C30 summary score.' representing a measure of cancer-specific health-related quality of life. The symptom scales/items that form part of the summary score will be reverse scored first to ensure that higher scores on the summary score reflect better outcomes. The H&N35 contains 35 items which comprise seven symptom scales and 11 symptom items.

The QLQ-C30 and H&N35 were collected at baseline, week 6 of treatment, and at 4 month and 14 month follow-up*.

Performance Status Scale for Head and Neck Cancer patients (PSS-HN):

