5.1.2 Secondary analysis of primary outcome

The difference between treatment group means at week 6 will be estimated using analysis of covariance (ANCOVA), adjusting for baseline OMWQ-HN. This will be on a complete case basis for those participants with a score at both baseline and 6 week visit. If the assumptions of the ANCOVA model are satisfied an adjusted mean difference between treatment groups at week 6 with 95% CI will be reported. This analysis is equivalent to analysing the change from baseline adjusted for baseline. The baseline and week 6 OMWQ-HN data will be presented graphically:

Example Figure 5: Spaghetti plot, OMWQ-HN score: change from baseline to week 6

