Data on the global, emotional, functional, physical, and total/composite scores will be summarised descriptively as mean, standard deviation, median, interquartile range and range at each time point for each of the treatment groups. The difference between treatment group mean total/composite score and mean global score at week 6 adjusted for the baseline of the score will be reported with 95% confidence intervals (only if the assumptions of the ANCOVA model are satisfied). This will be on a complete case basis for those participants with a score at both baseline and 6 week visit. A 95% confidence interval for the difference at 4 months will be reported if appropriate.

EORTC-QLQ-C30 (version 3.0) and EORTC-QLQ-H&N35 (version 3.0):

Procedures for scoring the scales and items of the QLQ-C30 and H&N35 will be in accordance with the published scoring manual [6]. Therefore, a scale’s score will only be calculated if at least half of its items are non-missing. The QLQ-C30 summary score will be computed as the mean of 13 scores from the QLQ-C30 (excluding the global health/QoL and financial difficulties scores) [7]. The symptom scales/items that form part of the summary score will be reverse scored first to ensure that higher scores on the summary score reflect better outcomes.

Data on the 21 outcome measures will be summarised descriptively as mean, standard deviation, median, interquartile range and range at each time point for each of the treatment groups. The difference between treatment group means for each of the 21 outcome measures at week 6 adjusted for the baseline of the outcome measure will be reported with 95% confidence intervals (only if the assumptions of the ANCOVA model are satisfied). This will be on a complete case basis (after pro-rating) for those participants with a score at both baseline and 6 week visit. A 95% confidence interval for the difference at 4 months will also be reported if appropriate.

Performance Status Scale for Head and Neck Cancer patients (PSS-HN):

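### The SAP reports baseline-adjusted week-6 differences only if ANCOVA assumptions hold, with no stated check or fallback, and applies this even to yes/no items whose residuals cannot be normal

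*SAP*

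**What the plan says.** SAP section 5.2 first gives an unconditional descriptive plan for the EORTC questionnaires: "Data on the 21 outcome measures will be summarised descriptively as mean, standard deviation, median, interquartile range and range at each time point". The baseline-adjusted week-6 difference is then promised only conditionally: each "outcome measure will be reported with 95% confidence intervals (only if the assumptions of the ANCOVA model are satisfied"). The MDADI total and global scores carry the same condition in the same section. For the primary instrument, section 5.1.2 says: "If the assumptions of the ANCOVA model are satisfied an adjusted mean difference between treatment groups at week 6" will be given with its interval. The SAP does not say which assumptions are examined, how, or what is reported if they fail. A 4-month interval is left to judgement without a criterion.

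Three neighbouring texts matter:

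- SAP 5.1.1 reports the unadjusted week-6 OMWQ-HN difference with its interval and attaches no condition.
- SAP 5.2 gives WHO grade III/IV as a difference in percentages with a 95% CI, and treats the PSS-HN subscales as ordinal.
- Protocol 16.1 says that problems with the assumptions of the primary-outcome regression models will be looked into, reported and dealt with. It plans no hypothesis tests for secondary outcomes.

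On the make-up of the measures, SAP 2.4.2 states: "The H&N35 contains 35 items which comprise seven symptom scales and 11 symptom items". Protocol Appendix 4 shows items 61 to 65 with No/Yes answers, among them "Have you used pain-killers" and "Have you used a feeding tube".

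**The concern.** A pre-specified plan should fix which treatment estimates will be shown. Here the decision rests on model diagnostics that the plan does not define, made once the data are in hand. For some measures the response format itself largely settles a strict check: the plan applies mean, SD and ANCOVA to two-valued scores, and may then withhold the difference because the model does not fit.

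The trial stopped at 87 of the 380 planned participants and tests no hypotheses on secondary outcomes, so estimates with intervals are the main thing these measures can contribute. The yes/no items cover pain-killers, supplements, tube use and weight change, which relate to the retained secondary objectives on pain control, nutrition and feeding-tube dependence (SAP 1.2.2). The dedicated tube and analgesic variables in SAP 5.2 are summarised by arm without a between-arm interval, so they do not fill the gap.

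**Working it through.** **1. The plan's count of 21.** SAP 5.2 says: "The QLQ-C30 summary score will be computed as the mean of 13 scores from the QLQ-C30 (excluding the global health/QoL and financial difficulties scores"). That leaves three QLQ-C30 measures: the summary score, global health and financial difficulties. Adding the H&N35 measures gives 3 + 7 scales + 11 single items = 21, which reproduces the plan's figure.

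**2. Response formats.** Items 61 to 65 are yes/no (5 measures). By subtraction, 11 − 5 = 6 H&N35 single items have four levels. Financial difficulties is also four-level, since for QLQ-C30 items other than global health the "possible question responses range from 1 (not at all) to 4 (very much"). That makes 7 four-level measures. As shares of the 21: yes/no 5/21 = 24%; all H&N35 single items 11/21 = 52%; all single-item measures including financial difficulties 12/21 = 57%.

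**3. Why yes/no items cannot have normal residuals.** The model contains arm (2 values) and baseline (2 values), so there are at most 2 × 2 = 4 fitted values. Each allows 2 outcomes, so there are at most 8 distinct residuals. Constant variance is not ruled out: if the probability p of a yes is the same in both arms and unrelated to baseline, p(1 − p) is constant.

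**4. Simulation of the condition.** ANCOVA of week-6 score on arm and baseline, 1,000 to 1,500 runs per setting. The documents give none of the following, so all are assumptions: total complete cases of 87, 70 or 50; latent baseline to week-6 correlation of 0.5; latent arm effect of 0 or 0.5 SD; several response distributions. Residuals were judged in two ways: Shapiro-Wilk p < 0.05, and a lenient rule (absolute skewness above 1 or absolute excess kurtosis above 2).

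| Measure type | Fails Shapiro-Wilk | Fails lenient rule |
|---|---|---|
| Yes/no item | 100% in every setting | 0.1% to 100% |
| Four-level item | 42% to 99.7% (n = 70 to 87); 28% to 93% (n = 50) | 0% to 41% |
| Multi-item scale | 9% to 99% | 0% to 40% |

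A test of constant residual variance failed in 1% to 38% of runs. The failure rate also moved with the treatment effect: for one four-level distribution at n = 87, Shapiro-Wilk failed in 87% of runs with no effect and 60% with an effect of 0.5 SD.

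**5. Expected number withheld under Shapiro-Wilk, n = 70 to 87.** Single-item measures only: 5 + 7 × 0.42 = 7.9 at the low end and 5 + 7 × 0.997 = 12.0 at the high end, that is 7.9/21 = 38% to 12.0/21 = 57%. Some multi-item scales would add to this. Under the lenient rule or a graphical judgement the number could fall to none.

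**6. Would the withheld intervals have been poor?** Coverage of the ordinary ANCOVA 95% interval was 93.5% to 98.0% in all settings. Failing a normality check was therefore a bad guide to whether the interval could be used.

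**The case against.** The strongest reply is that the failure rates belong to checks chosen here, not to the SAP. A statistician who looks at residual plots and tolerates coarse scores might report all 21 differences. That stands, and it is why the size can only be given as a range.

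A reader might infer that about half of the 21 measures will get no treatment comparison, whatever the laser does. The documents do not support this, for three reasons:

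- About half is a count of single-item measures, not of measures shown to fail.
- All 21 are summarised by arm at every time point whatever the diagnostics show. A crude difference can be worked out from those summaries; for a yes/no item scored 0 or 100, the mean is simply the percentage answering yes.
- The failure rate is not independent of the effect, as the 87% against 60% comparison shows.

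Nor is the primary result at risk: the unadjusted OMWQ-HN difference in SAP 5.1.1 is unconditional. It is also fair that the secondary outcomes are unpowered and mainly descriptive, and that dedicated tube, weight and analgesic variables partly duplicate items 61 to 65.

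Two objections to the remedy are partly right. A heteroscedasticity-robust interval deals with unequal variance, not non-normality; but the coverage above suggests that non-normality does little harm at these sample sizes. A simple percentage difference gives up baseline adjustment for the yes/no items.

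None of this answers the central point: the condition is in the plan, the check is undefined, and nothing is put in place of a withheld estimate.

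**Conclusion.** The point holds in a limited form. The adjusted week-6 difference and its interval are conditional, without a stated check or fallback, for 21 EORTC measures, two MDADI scores and the secondary OMWQ-HN analysis. Five of the EORTC measures cannot satisfy normality at all. Under a formal normality test roughly 8 to 12 of the 12 single-item measures would be withheld, plus some scales; under a looser reading, possibly none. The loss is confined to the adjusted week-6 estimates. It should be corrected because the rule can suppress usable intervals and lets the data decide what is shown.

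The figures rest on assumed complete-case numbers, correlation and response distributions, so the ranges are illustrations and not bounds. They also assume that items 61 to 65 are all scored as single items with the format in Appendix 4 of the supplied protocol (version 2.1). The SAP refers to protocol version 4.0.

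**What to change.** - In SAP 5.1.2 and 5.2, delete the condition on the ANCOVA assumptions. Always report the baseline-adjusted week-6 difference with a bootstrap or heteroscedasticity-robust 95% CI, and describe any lack of fit as a caveat beside the estimate.
- For H&N35 items 61 to 65, replace mean, SD and ANCOVA with n (%) by arm and the difference in percentages with a 95% CI, in the form that SAP 5.2 already uses for WHO grade III/IV.

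The cost is SAP wording and a few lines of Stata code; no new data are needed. Intervals may be slightly wider, and the yes/no items lose their baseline adjustment.

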7. BACKGROUND

Around 4000 patients per year in England and Wales [1] undergo chemotherapy or radiotherapy (C)RT for head and neck cancer (HNC). 97% of these patients will develop oral mucositis [2].

Oral mucositis (OM) is a debilitating, painful complication characterised by inflammation of the mucous membranes, erythema and ulceration [3]. The tissue inside the mouth can feel as though it has been burnt, with ulcers developing on the mouth lining, tongue and lips. These ulcers can become infected with bacteria in the mouth. The infection can spread to the blood and other organs (sepsis) which can be life threatening. Thus patients with OM are likely to find that their ability to talk, eat and drink is profoundly affected. Swallowing difficulty (dysphagia) is the major determinant of post treatment quality of life [4].

Over 90% of patients need nutritional support for severe dysphagia during and after (C)RT[5]. Weight loss has been shown to lead to poorer survival, and longer periods without food or drink increase the likelihood of long term dysphagia and dependency on tube feeding [6]. The feeding tube can be inserted through the nose or directly into the stomach. To start the feeding and control pain, patients require hospital admission for several days. Feeding tubes can lead to distress and isolation as patients often do not want to be seen in public with a feeding tube in place. Insertion of feeding tubes has a complication rate of 5-15%, and a mortality rate of around 2% [7]. Long-term tube feeding is an independent predictor of long-term quality of life [5] and increased use of painkillers (analgesics).

Mucositis is an independent risk factor for pharyngo-oesophageal stricture. This is a devastating complication which can develop after HNC radiotherapy. A ring of scarring partially or completely blocks the gullet. This can result in the inability to swallow, aspiration and dependence on a feeding tube [8,9].

OM is a predictable side effect of (C)RT treatment, but current management varies across the UK depending on the funding available. Current treatment for OM includes patient education through reinforcing the importance of good oral hygiene, hydration as well as providing nutritional advice and pain management using analgesics, mouthwashes and coating gels. It is determined by the level of side effects that the patient is experiencing and which drugs are available on local formularies.

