9.3 Outcome Measures

9.3.1 Primary outcome measure

Primary Outcome: OMWQ-HN score at week 6 following start of LLLT treatment.

9.3.2 Secondary outcome measures:

- OMWQ-HN and WHO mucositis scores collected at baseline and weekly during weeks 1-6 of treatment.
- Long term reported health related quality of life as measured by EORTC QLQ C30 (version 3.0),
 EORTC QLQ C30/H&N 35 (EORTC QOL Module for Head and Neck Cancer) and the EQ-5D-5L at baseline, week 6, month 4 and month 14, and MDADI at baseline, week 6, month 4 and month 14.
- Nutritional Parameters as measured by Performance Status Scale's (PSS-HN) collected weekly
 at baseline, weeks 1-6, month 4 and month 14. Recording of weekly weight changes from
 baseline during treatment, the quantity of enteral nutrition consumed, number of days of
 feeding tube in situ.
- Changes in swallowing function measured by the timed water swallow test collected at baseline, week 6 of LLLT month 4 and month 14.
- Pain outcomes as measured by use of analgesics/ topical treatment and pain domain of EQ 5D-5L and OMWQ-HN at randomisation and weekly to week 6 during treatment.

 Safety, specifically adverse events attributed to LLLT and clinical complications notably number of days as inpatient hospital admissions and interruptions in CRT treatment (recorded weekly 1-6 during treatment).

• Clinical outcomes specifically patient survival, quality-adjusted survival recurrence and persistence of disease at 14 months.

Economic outcomes:

- Incremental cost per change in OMWQ-HN score recorded between baseline and at week 6 of therapy and incremental cost per QALY over 14 months
- Quality-adjusted life years based upon EQ-5D-5L [14] and EORTC-8D [15] utility scores measured at baseline, week 6 and 4 and 14 months
- Costs associated with treatment (weeks 0-6) will be collected weekly via the eCRFs
 (e.g. adverse events and use of analgesics)
- Health care utilisation based on responses to Health Utilisation Questionnaire administered at 4 and 14 months (assessing: visits to the GP/walk-in clinic/A&E etc.)
- Participant and family costs collected via the Time and Travel Questionnaire administered at 14 months
- Total costs of LLLT and sham LLLT measured at 4 and 14 months, from the perspective of the NHS and personal and social services to participants and families

Qualitative outcomes as identified through:

- Observations of training
- Interviews with health professionals delivering LLLT

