Quality adjusted survival analyses will be carried out to simultaneously assess quality and survival functions. A Quality function, based on the EQ5D global score, will be estimated at each survival event time using interpolation, and the survival distribution down-weighted by any negative quality function. The area under each of the survival and quality adjusted survival curves will be presented as (with 95%CI).

Long term data will be presented graphically including proportions of positive and negative changes from baseline. Standardised area under the curve analysis will be used to describe longitudinal quality of life scores. Exploratory, descriptive hierarchical modelling, not based on significance testing, may be used to explore repeated measures nested within patients accounting for important baseline clinical confounders and stratification factors.

Hypothesis testing is not planned for the analyses of secondary outcome measures.

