1.2.2 Secondary objectives

- Determine the effectiveness of LLLT in preventing severe OM during RT or CRT for HNC as measured by WHO mucositis scores.
- Apply evidence derived from the trial to inform NHS guidance in the use of LLLT for managing OM.
- Investigate the short and long term benefits to patients in terms of dependence on feeding tubes, nutritional status, pain control, admission to hospital, treatment interruptions and swallowing function and quality of life.

- Investigate the long term risks of LLLT (survival, recurrence, disease progression).
- Identify barriers and facilitators to implementing LLLT in routine clinical care through a qualitative process evaluation.

See protocol version 4.0 for further objectives associated with the economic and qualitative sub studies.

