The PSS-HN [8] is a 3-item scale designed to evaluate functional performance of H&N cancer patients, specifically Normalcy of Diet, Eating in Public, and Understandability of Speech. Each item is scored on an ordinal scale ranging from 0 to 100, with higher scores representing better functional performance. The Normalcy of Diet item has 11 ordinal categories which range from 0 to 100 in increments of 10, and both the Understandability of Speech and Eating in Public items have five ordinal categories: 0, 25, 50, 75, 100. For the Eating in Public item, participants who were inpatient at the time of the questionnaire were coded into a separate category.

The PSS-HN was collected at baseline, weekly during weeks 1 to 6 of treatment, and at 4 month and 14 month follow-up*.

Oral intake and tube dependency:

Data on participants' oral intake (measured as a percentage relative to their normal (i.e., pre-illness) levels of intake), level of dependency on feeding tube, whether enteral feeding was initiated, type of feeding tube used, and number of days the feeding tube was used in the past week were collected weekly during weeks 1 – 6 of treatment, and at 4 month and 14 month follow-up*.

Weight and Body Mass Index (BMI):

Weight data were collected at baseline, weekly during weeks 1 to 6 of treatment, and at 4 month and 14 month follow-up*.

Timed water swallow test (WST):

The WST [9] provides an indication of overall swallowing performance. Participants were tasked to drink 100 mL of water where they were timed (in seconds) and the number of swallows taken was recorded. The test was not performed in participants who must remain nil by mouth, who automatically scored 0 for the test. If there were overt signs of significant aspiration (explosive coughing, prolonged coughing) or the patient became distressed, the assessment was stopped and the remaining amount in the cup was measured and recorded.

The WST was collected at baseline, week 6 of treatment, and at 4 month and 14 month follow-up*.

Pain Outcomes:

The outcomes used to measure pain are: the use of analgesics/ topical treatment, the pain/discomfort domain of the EQ-5D-5L, and the OMWQ-HN (see primary outcome measure section for OMWQ-HN). There are also pain specific subscales in both the QLQ-C30 and the H&N35.

Analgesics, topical treatment, and visits to oral hygienist (other than for laser treatment):

Analgesics: whether participants had used painkillers in the last week, and the type of pain killers.

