4.2 Baseline characteristics

Demographic, clinical and baseline characteristics and trial stratification factors: type of planned treatment (radiotherapy alone/chemo-radiotherapy) and type of radiotherapy field (unilateral/bilateral) at randomisation will be summarised across treatment groups descriptively. We will report the number and percentage in each group for all categorical variables (e.g. gender) and mean, SD or median, IQR and range, as appropriate, for all continuous variables. No significance testing will be carried out due to the randomised nature of the study.

Example Table 7: Baseline characteristics

	Sham (n=xx)	Laser (n=xx)	Overall (n=xx)
Age (years), mean (SD)			
Height (cm), mean (SD)			
Weight (kg), mean (SD)			
Gender			
Female			
Male			
Type of planned treatment			
Radiotherapy alone			
Chemo-radiotherapy			
Type of radiotherapy field			
Unilateral			
Bilateral			
Site of disease			
Nasopharynx			
Oropharynx-HPV positive			
Oropharynx-HPV negative			
Oropharynx-HPV undetermined			
Larynx			
Oral			
Unknown Primary			
Missing			
TNM Classification			
Primary Tumour			
TX			
T0			
Tis			
T1			
T2			
T3			
T4			
Missing			
Regional Lymph Nodes			
NX			
NO			
N1			
N2			
N3			
Missing			

Distant Metastasis MX MO M1 Missing			
Patient to receive chemotherapy in addition to radiotherapy? No Yes Missing			
How will the chemotherapy be administered? Concurrent Induction Induction and Concurrent NA Missing			
Patient to have IMRT No Yes			
Patient has had surgery to primary tumour No Yes Missing			
Adult Co-morbidity evaluation (ace-27) None Grade 1 - Mild Decompensation Grade 2 - Moderate Decompensation Grade 3 – Severe Decompensation Unknown Missing			
WHO Mucositis Scale 0 (none) I (mild) II (moderate) III (severe) IV (life-threatening) Missing			

Data are n; %, mean (SD) or median (IQR); range, unless otherwise stated

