Data will be summarised descriptively, by subscale, as the frequency and percentage of each score category at each time point for each of the treatment groups. Given there were only 87 patients randomised in total and the frequency tables will have either 22 cells (11 categories by 2 treatment groups) or 10 cells (5 categories by 2 treatment groups) it may be necessary to summarise the data as the frequency and percentage of participants scoring ≤ 50 for the subscale [14, 15]. As these subscales are made up of ordinal categories, the median and range will also be presented.

Oral intake and tube dependency:

Data on the oral intake, feeding tube dependency, whether enteral feeding was initiated, and type of feeding tube will be summarised descriptively as the frequency and percentage at each time point for each of the treatment groups. Data on the number of days the feeding tube was used in the past week will be described using appropriate summary statistics.

Weight and Body Mass Index (BMI):

BMI scores at each time point will be calculated using height data collected at baseline and weight collected at each time point. Data on weight and BMI will be summarised descriptively as mean, standard deviation, median, interquartile range, observed range at each time point for each of the treatment groups.

Timed water swallow test (WST):

Measures of swallow capacity (mL/time taken), swallow volume (mL/number of swallows), and swallow speed (time taken/number of swallows) will be derived from the data.

Data on swallow capacity, volume, and speed will be summarised descriptively as mean, standard deviation, median, interquartile range, observed range at each time point for each of the treatment groups.

Pain outcomes

OMWQ-HN will be summarised numerically as mean, standard deviation, median, interquartile range, and range at each time point (baseline to week 6) for each of the treatment groups [as above].

EQ-5D-5L pain/discomfort domain will be summarised as median, interquartile range, and range [16].at baseline and week 6 only for each of the treatment groups

Analgesics, topical treatment, and visits to oral hygienist (other than for laser treatment)

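### SAP 5.2 summarises raw weight and BMI visit by visit and never derives the within-patient weight change that Protocol 9.3.2 lists among its nutritional parameters

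*SAP*

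**What the plan says.** Protocol 9.3.2 groups several measures under nutritional parameters: PSS-HN, weight, quantity of enteral nutrition and days with a feeding tube. The weight item is "Recording of weekly weight changes from baseline during treatment". The SAP keeps the matching objective in 1.2.2, which covers "dependence on feeding tubes, nutritional status, pain control" among other benefits. Protocol section 7 gives a reason for interest in weight: "Weight loss has been shown to lead to poorer survival".

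On data, SAP 2.4.2 states "Weight data were collected at baseline, weekly during weeks 1 to 6 of treatment, and at 4 month and 14 month" follow-up, the last only for participants who began laser therapy before 6 July 2018. On analysis, SAP 5.2 states "Data on weight and BMI will be summarised descriptively as mean, standard deviation, median, interquartile range, observed range at each time point", by treatment group. BMI is derived from baseline height, so it carries no further information on change. SAP 3.2 and 5.5 include in each summary those who attended that visit and have evaluable data. Baseline weight by arm also appears in Example Table 7.

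Elsewhere the SAP does use baseline. It gives baseline-adjusted week-6 differences with 95% CIs for MDADI and the EORTC measures (5.2) and, as a secondary analysis, for OMWQ-HN (5.1.2).

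**The concern.** The protocol's weight measure is a change within each patient. The SAP's is a level, described separately at each visit, and the SAP gives no reason for the difference. Adults differ in weight by far more than most would be expected to lose over six weeks, so a comparison of week-6 means largely reflects who was randomised to which arm. The mean can also move between visits because different people attend, with no individual changing weight. What is at stake is whether the trial can describe, with usable precision, any effect of LLLT on weight loss during treatment.

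**Working it through.** **Figures in the documents.** Neither document gives an SD, correlation or target effect for weight. The only power inputs are for OMWQ-HN: a difference of 4 points, SD 10.7, two-sided 5% and 90% power. They reproduce: 2 × (1.960 + 1.282)² × 10.7² / 4² ≈ 150.4, so 151 per arm by the normal approximation and 152 with the t correction. Then 152 / 0.80 = 190. This does not bear on weight, so the calculations below rest on assumed ranges.

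**Inputs.** From SAP 2.6, 87 were randomised, 1:1, so about 43 per arm. With the planned 20% loss, 0.80 × 43.5 ≈ 35 per arm. Assumed: weight SD 14-18 kg, equal at both visits, and baseline to week-6 correlation r of 0.90-0.97.

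**Formulas for the SE of an arm difference at week 6**
- Raw weight: SD × √(2/n)
- Change from baseline: SD × √(2(1−r)) × √(2/n)
- Adjusted for baseline: SD × √(1−r²) × √(2/n)

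Half-width of the 95% CI is 1.96 × SE, in kg:

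| SD | n per arm | r | Raw | Change | Adjusted |
|---|---|---|---|---|---|
| 14 | 43 | 0.97 | 5.92 | 1.45 | 1.44 |
| 14 | 43 | 0.90 | 5.92 | 2.65 | 2.58 |
| 18 | 35 | 0.97 | 8.43 | 2.07 | 2.05 |
| 18 | 35 | 0.90 | 8.43 | 3.77 | 3.68 |

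For example, 14 × √(2/43) = 3.02 and 1.96 × 3.02 = 5.92; then 5.92 × √0.06 = 1.45. The interval on change is narrower by 1/√(2(1−r)), which is 2.2 to 4.1 times and depends only on the assumed r.

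**Second set of assumptions.** Take weight SD 12-18 kg and specify the SD of six-week change directly as 3-5 kg, with 43 and 44 patients. The half-width is 5.0-7.6 kg on raw weight and 1.3-2.1 kg on change. Under the same weight SDs, chance alone gives a baseline gap between arms above 2 kg in 44-60% of trials.

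**Can the reader subtract the reported means?** If the same patients contribute at both visits, subtraction recovers the difference in mean change exactly, though not its SD or CI. Suppose instead that about 43.5 per arm contribute at baseline and 35 at week 6, missing at random. The change in who is included then adds an SE of SD × √(2 × (1/35 − 1/43.5)) = SD × 0.106, or 1.3-1.9 kg for SD 12-18. The SE of the paired change itself is 3 to 5 × √(2/35) = 0.7-1.2 kg. Treating the two as independent, the subtraction has an SE of √(0.72² + 1.27²) = 1.5 kg to √(1.20² + 1.90²) = 2.2 kg, none of which the planned tables would show.

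**At 14 months.** Only participants who started laser therapy before 6 July 2018 have data, while the baseline mean covers the whole arm. Subtraction then compares different groups by design.

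**The case against.** The strongest reply is that secondary outcomes are descriptive. Protocol 16.1 plans no hypothesis tests for them, the trial closed at 87 of 380, and no conclusion depends on a weight comparison. The SAP plans no arm difference for weight at all, so the half-widths above belong to a contrast that readers would draw for themselves. Weight is not singled out either: PSS-HN, the swallow test and tube days also lack baseline adjustment. All of this stands. It limits the importance of the point but does not explain why the description is of a level when the protocol names a change.

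The version also matters. The SAP works to protocol version 4.0, and the protocol supplied is 2.1, so whether the wording on change survived cannot be checked. Even in 2.1, the assessment list and schedule (13.6, 13.7) speak only of recording weight and BMI. Protocol 16.1 does say "Long term data will be presented graphically including proportions of positive and negative changes from baseline", but that sentence is not specific to weight.

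Three stronger readings are tempting and are not supported:
- **That the nutritional objective goes unassessed.** Weight is one of several nutritional parameters, and SAP 5.2 also summarises PSS-HN, oral intake and tube use. The expected benefits in Protocol section 7 mention improved nutrition, not weight.
- **That the tables can show nothing about weight loss.** Baseline weight is reported by arm and completeness by visit, so an imbalance is visible and mean change can be approximated.
- **That body size would swamp any effect.** The documents give no weight SD or target effect, so this cannot be established.

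**Conclusion.** The mismatch is real and modest. Against protocol version 2.1, the SAP has no analysis of within-patient weight change and gives no reason for leaving it out. Raw visit means, even when subtracted, carry no SD or CI and are distorted when different patients contribute at each visit. Under the assumed SD of 14-18 kg, correlation of 0.90-0.97 and 35-43 per arm, a week-6 arm difference would be known to about ±6-8 kg on raw weight and about ±1.5-4 kg on change. On those values raw weight would be likely to obscure a difference of a few kilograms. The size of the gain depends on assumptions that are not in the documents; its direction does not, for any correlation above 0.5. The primary outcome and the trial's main conclusion are unaffected.

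**What to change.** In the weight and BMI paragraph of SAP 5.2:

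- Add change from baseline in weight, in kg and percent, with mean and SD, by arm, at each of weeks 1-6, in participants with both values, giving the number contributing.
- Report the week-6 between-arm difference adjusted for baseline weight with 95% CI, subject to the same check of model assumptions that the SAP applies to MDADI and the EORTC scores, and without a hypothesis test.
- Optionally, describe change at 4 and 14 months in participants with both values. The protocol's weight item covers only the treatment period.
- Keep raw weight and BMI as background.

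If version 4.0 of the protocol dropped weight change as an outcome, one sentence in the SAP saying so and why would be the alternative. The cost is a few lines of SAP text and one derived variable, since baseline and weekly weights are already collected.
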